PROTOCOL TITLE: Assessment of Measurement Variability Across Automated Biometry Devices

PROTOCOL # 005

STUDY TREATMENTS: Non-interventional (None)

Background:

Some intraocular surgeries depend on accurate white-to-white (WTW), corneal thickness (CT) and anterior chamber depth measurements (ACD) for optimal outcomes.

Scientific Rationale:

Some intraocular surgeries require accurate WTW, CT, and ACD measurements. Previously, the Orbscan II was used to calculate the positioning characteristics for, and selection of, some phakic intraocular lenses, but newer devices are now available. Variability in the measurements with these newer devices may impact the surgical outcomes for formulas originally based on the Orbscan II. This study aims to determine how the newer devices correlate with measurements obtained with the Orbscan II.

Clinical Hypothesis:

Different biometers/topographers measure WTW, CT, and ACD differently than the Orbscan II.

Study Objectives:

The objective of this study is to determine the correlation of WTW, CT, and ACD measurements from the Orbscan II to a variety of readily available biometric devices.

OVERALL STUDY DESIGN

This is a non-interventional prospective, single center, bilateral, comparative study of WTW, CT, and ACD measurements as taken on the Orbscan II compared to the IOL Master 700 (Zeiss), IOL Master 500 (Zeiss), Atlass 9000 (Zeiss), Lenstar 900 (Haag-Streit), Argos (Alcon), iTrace (Tracey), Pentacam (Oculus), and manual calipers. Additional biometric devices or external photographs may be included as well.

Duration:

3 months or longer to meet required enrollment

Administration:

Patients with healthy eyes who meet the inclusion criteria will be offered the opportunity to participate in the study.

Visit Schedule:

All subjects will undergo 1 visit. At the study visit, after informed consent, the subjects' demographic information will be collected, and the subject will have the following testing:

- 1) Orbscan II (ACD/WTW/CT)
- 2) IOL Master 700 (ACD/WTW/CT)
- 3) IOL Master 500 (ACD/WTW/CT)
- 4) Atlas 9000 (WTW)
- 5) Lenstar 900 (ACD/WTW/CT)
- 6) Pentacam (ACD/WTW/CT)
- 7) iTrace (WTW/CT)
- 8) Argos (ACD/WTW/CT)
- 9) Manual caliper measurement (WTW)
- 10) Additional biometric devices or external photographs may be included as well

STUDY POPULATION CHARACTERISTICS:

Condition

Myopic patients with a spherical equivalent of at least -1.00D with healthy eyes and no prior eye surgery

Number of Subjects:

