Under the assumption that the average WTW on the Orbscan II is 11.65 mm¹ and the average WTW on the IOL Master is 11.76 mm and the Pentacam WTW is 11.61 mm², then 168 eyes would be required, for a total of 336 eyes. Other biometers are assumed to have similar averages. The standard deviation for each measurement is 0.36 for the Orbscan II, and a power of 80% and Type I error probability of 0.05 was targeted.³

ACD measurements should be statistically similar to WTW measurements.

There are limitations to including both eyes from a single volunteer due to symmetry between eyes. As such, the proposed total number of patients is 200, which allows 400 eyes and 200 different data points assuming relative symmetry between the eyes. To this author's knowledge, this would be the largest comparative study to date of WTW, ACD, and CT measurements.

3. Rosner B. Fundamentals of Biostatistics. 7th ed. Boston, MA: Brooks/Cole; 2011.

Inclusions:

- 1) Adults ages 18-50 years of age with healthy eyes and no prior ocular surgery.
- 2) At least -1.00 D of myopia (spherical equivalent).
- 3) Able to comprehend and willing to sign informed consent and complete all required testing procedures
- 4) Clear intraocular media

Exclusions:

Subjects will not be permitted to enroll in this study if they meet any of the following exclusion criteria:

- 1) Any corneal abnormality, other than regular corneal astigmatism (as determined by pre-operative testing) that in the opinion of the investigator would confound the outcome(s) of the study
- 2) History of or current retinal conditions or predisposition to retinal conditions
- 3) Amblyopia or strabismus in either eye
- 4) History of or current anterior or posterior segment inflammation of any etiology
- 5) Any form of neovascularization on or within the eye
- 6) Glaucoma (uncontrolled or controlled with medication)
- 7) Optic nerve atrophy
- 8) Subjects with diagnosed degenerative eye disorders

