- 9) Subjects who have an acute or chronic disease or illness that would confound the results of this investigation in the opinion of the principal investigator (e.g. connective tissue disease, immunocompromised, clinically significant atopic disease, etc.)

EVALUATION CRITERIA:

The main objective of this study is to determine the standard difference of WTW, ACD, and CT of various biometric devices compared to the Orbscan II.

Primary Clinical Endpoints:

The determination of the degree of correlation of WTW, ACD, and CT measurements between various biometric devices.

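### The main objective (an undefined standard difference) and the primary endpoint (correlation) cannot show whether a device's difference from the Orbscan II changes with eye size

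*Combined protocol and SAP*

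**What the plan says.** The Scientific Rationale explains that "the Orbscan II was used to calculate the positioning characteristics for, and selection of, some phakic intraocular lenses", and then warns: "Variability in the measurements with these newer devices may impact the surgical outcomes for formulas originally based on the Orbscan II". The Study Objectives section asks for the correlation of each device with the Orbscan II.

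Evaluation Criteria words the main objective differently, as being to "determine the standard difference of WTW, ACD, and CT of various biometric devices compared to the Orbscan II". *Standard difference* is not defined. The primary endpoint, in the same section, is "The determination of the degree of correlation of WTW, ACD, and CT measurements between various biometric devices".

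Number of Subjects sizes the study on mean WTW: it assumes that "the average WTW on the Orbscan II is 11.65 mm", against 11.76 mm for the IOL Master and 11.61 mm for the Pentacam, with an SD of 0.36 given for the Orbscan II only. Enrolment is 200 patients (400 eyes).

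The documents plan no limits of agreement, no slope, no conversion equation and no check of whether the difference varies with the size of the measurement.

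**The concern.** If formulas were built on Orbscan II readings and surgeons now hold other devices, the question is how far each device departs from the Orbscan II, eye by eye and across the range of eyes. Use of newer-device readings in those formulas is implied by the rationale, not stated.

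Neither planned summary answers that question. A mean difference averages over all eyes, so an over-reading in large eyes and an under-reading in small ones cancel. A correlation coefficient does not change when one device's readings are shifted or multiplied by a constant, so it cannot reveal an offset or a scale difference. Neither one on its own describes how far individual eyes scatter around the average difference.

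The study could thus meet its objective and endpoint in full, and a device could look interchangeable with the Orbscan II while differing at both ends of the range. Those ends are where a formula input is furthest from average. The paired data would already hold the answer.

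**Working it through.** **1. The plan's own figure.** Inputs from Number of Subjects: difference 11.76 − 11.65 = 0.11 mm, SD 0.36, power 80%, alpha 0.05 (two-sided reproduces the figure).

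n per group = 2 × [0.36 × (1.960 + 0.842) / 0.11]² = 168.1

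This matches the stated 168 eyes (336 in total). The study was sized for a difference between two independent means, and nothing in that calculation concerns scale or individual agreement. The second assumed difference, for the Pentacam, is 11.61 − 11.65 = −0.04 mm.

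**2. What the planned summaries can see.** Let T be true size, Orbscan II reading O = T + error, and device reading D = a + kT + error. The mean difference is a + (k − 1) × mean(T), which can be 0 when k is not 1. The correlation is unchanged if D is rescaled or shifted. Neither quantity identifies k.

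**3. Illustration.** Assumed, because the documents give none of it: k = 1.10, mean difference 0, 90% of Orbscan II variance is true variation between eyes, and equal error variance in both devices.

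- Var(O) = 0.36² = 0.1296; Var(T) = 0.90 × 0.1296 = 0.1166; error variance = 0.0130
- Var(D) = 1.21 × 0.1166 + 0.0130 = 0.1541
- Cov(O, D) = 1.10 × 0.1166 = 0.1283
- Correlation = 0.1283 / √(0.1296 × 0.1541) = 0.91
- Mean difference = 0
- Discrepancy at 2 SD = 0.10 × 2 × 0.36 = 0.072 mm, positive in large eyes and negative in small ones (0.068 mm if 2 SD of true size is used, √0.1166 = 0.342)

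So about 0.07 mm at each end, with a mean difference of zero and a correlation of 0.91.

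**4. What the difference-on-average regression would show.**

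- Slope = [(0.1541 − 0.1296)/2] / [(0.1296 + 0.1541 + 2 × 0.1283)/4] = 0.01225 / 0.1351 = 0.091
- Var(D − O) = 0.1296 + 0.1541 − 2 × 0.1283 = 0.0271, so SD = 0.165 mm and 95% limits of agreement are about ±1.96 × 0.165 = ±0.32 mm
- Residual variance = 0.0271 − 0.091² × 0.1351 = 0.0260
- SE of slope, 200 subjects with one eye each = √[0.0260 / (198 × 0.1351)] = 0.031
- z = 0.0907 / 0.0312 = 2.91; power = Φ(2.91 − 1.96) = 0.83 (a simulation of 20,000 studies gave 82%)

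The same formulas with other assumed shares of true variance:

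| Share of true variance | Correlation | Slope | SE | Power |
|---|---|---|---|---|
| 0.80 | 0.81 | 0.086 | 0.045 | 47% |
| 0.90 | 0.91 | 0.091 | 0.031 | 83% |
| 0.95 | 0.95 | 0.093 | 0.022 | 99% |

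The planned enrolment is adequate for a 10% scale difference when correlation is about 0.9 or higher, and weaker below that.

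**The case against.** Four points can be made for the plan.

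- **It does not rest on a difference alone.** Correlation is both the primary endpoint and the stated objective. That is true, but correlation cannot fill this gap, for the reason in step 2.
- ***Standard difference* might mean more than a mean difference.** It could be a standardized difference or the SD of differences. The latter would supply the spread, but no reading supplies a check against eye size.
- **Routine descriptive tables would give each device's SD, from which the slope could be rebuilt.** Possibly, but the plan does not name those outputs or that use.
- **The difference may well be constant.** That stands: nothing in the documents shows otherwise.

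A reader might go further and infer that a single difference necessarily misconverts eyes away from the mean, because the regression slope of Orbscan II on device equals the correlation when SDs are equal. At 2 SD (0.72 mm) this would give (1 − r) × 0.72 = 0.144, 0.072 and 0.036 mm at r = 0.80, 0.90 and 0.95. That does not hold up. If both devices read the same true size with equal independent error, two Orbscan II readings of the same eye show the same gaps, grouping by true size removes them, and the slope of difference on average is 0. It is regression to the mean, not device disagreement. Converting readings by that slope before using a formula calibrated on noisy Orbscan II readings would shrink them twice: r × (r − 1) × 0.72 = −0.115, −0.065 and −0.034 mm.

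Nor do the documents say that a constant offset will be published or applied as a correction.

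**Conclusion.** The concern holds as a gap in the planned analysis. The main objective is undefined, the primary endpoint is blind to offset and scale, and neither can show a difference that varies with eye size, although the rationale depends on how newer devices stand in for the Orbscan II.

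The size of any effect is unknown. Under the assumed 10% scale difference it is about 0.07 mm at 2 SD of WTW. That is larger than the 0.04 mm mean difference assumed for the Pentacam and about two thirds of the 0.11 mm for the IOL Master (0.072 / 0.11 = 0.65). With a true scale factor of 1 it is zero. The illustration covers WTW only, because the documents give no means or SDs for ACD or CT. It shows an unexamined risk, not an error in any named device.

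**What to change.** Define *standard difference* as the paired difference, device minus Orbscan II, and align the objective and the primary endpoint with it. For each device and each measure it provides, prespecify as the main analysis:

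- the mean difference with 95% CI;
- 95% limits of agreement;
- a regression of the difference on the two-device average, reporting the slope with 95% CI;
- allowance for two eyes per subject throughout, for example a subject random effect.

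Keep correlation as secondary. Describe a device as differing by a constant only where the slope and its CI support that, judged on the width of the interval and not only on whether it includes 0. Otherwise report the difference across the observed range. Any conversion equation should be secondary and come from a method that allows for error in both devices, such as Deming regression, with the assumed ratio of error variances stated and varied. The same caution applies to the slope itself, since unequal error variances can also move it from 0.

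The cost is a revised analysis section and a little more analysis. Subjects, scans and data are unchanged.

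### The only primary endpoint is a correlation, but the hypothesis, main objective and sample size concern a difference from the Orbscan II, and no analysis of differences is specified

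*Combined protocol and SAP*

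**What the plan says.** The document states its aim in several places, and they do not agree.

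**Difference from the Orbscan II**
- Clinical Hypothesis: "Different biometers/topographers measure WTW, CT, and ACD differently than the Orbscan II".
- Evaluation Criteria, main objective: to "determine the standard difference of WTW, ACD, and CT of various biometric devices compared to the Orbscan II". The term *standard difference* is not defined.
- Number of Subjects: the calculation compares mean WTW values. The Orbscan II mean is 11.65 mm, and "the average WTW on the IOL Master is 11.76 mm and the Pentacam WTW is 11.61 mm". On spread it says "The standard deviation for each measurement is 0.36 for the Orbscan II". Power is 80% and type I error 0.05. No correlation enters the calculation.

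**Correlation**
- Study Objectives: "The objective of this study is to determine the correlation of WTW, CT, and ACD measurements from the Orbscan II", against a range of other devices. The last sentence of the Scientific Rationale states a similar aim.
- Primary Clinical Endpoints, the only endpoint listed: "The determination of the degree of correlation of WTW, ACD, and CT measurements between various biometric devices". It does not name the Orbscan II as reference.

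There is no analysis section. The document names no correlation coefficient, paired test, confidence interval or limits of agreement. It gives no method for two eyes per patient beyond saying that 200 patients "allows 400 eyes and 200 different data points assuming relative symmetry between the eyes".

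**The concern.** Correlation and difference are separate properties of a pair of devices. Correlation shows whether eyes that read large on one device also read large on the other. It does not show whether the two devices give the same number.

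The practical reason for the study is that "Variability in the measurements with these newer devices may impact the surgical outcomes for formulas originally based on the Orbscan II". To judge that, a user needs to know, for each device, how far it reads from the Orbscan II on average and how much that gap varies from eye to eye, both in mm. Correlation has some use here, since it indicates how well an Orbscan II value could be predicted from another device. As the sole primary endpoint, however, it could be high for every device whether or not the hypothesis is true. Because the analysis is unspecified, the choice of coefficient, and whether differences are reported at all, could also be made after the data are seen.

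**Working it through.** **1. What the sample size was built for.** Inputs from Number of Subjects: difference 11.76 − 11.65 = 0.11 mm, SD 0.36 mm, α 0.05 (two-sided assumed), power 80%. For two independent means:

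n per group = 2 × 0.36² × (1.960 + 0.842)² / 0.11² = 168.1

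With z values rounded to 1.96 and 0.84 the result is 167.9. This matches the stated 168 (336 in total). A one-sided test gives 133, and the Pentacam difference of 0.04 mm gives 1272. The study was therefore sized for a 0.11 mm difference in means.

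**2. Effect of an offset on correlation.** Adding a constant to one device changes neither its deviations from its own mean nor its ranks, so Pearson and rank correlations are unchanged. In simulated data with SD 0.36 mm and r = 0.90, offsets of 0, 0.11, 0.5 and 1.0 mm all left r at 0.90, while the mean difference moved to about 0, 0.11, 0.50 and 1.00 mm.

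**3. If an agreement coefficient were meant.** With equal SDs, concordance = 2r·SD² / (2·SD² + d²). At r = 0.90 and d = 0.11:

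2 × 0.90 × 0.1296 / (0.2592 + 0.0121) = 0.86

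It falls only from 0.90 to 0.86 and gives no bias in mm.

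**4. What the paired data can deliver.** The documents give neither an SD of differences nor a between-device correlation r. Here r is assumed over a range, and 0.36 mm is applied to both devices. Formulas, with n = 200 patients and one data point each:
- SD of differences, SDd = 0.36 × √(2(1 − r))
- limits of agreement = bias ± 1.96 × SDd
- CI half-width of the mean difference = 1.96 × SDd / √200
- CI half-width of each limit = 1.96 × √(1/200 + 1.96²/(2 × 199)) × SDd = 0.237 × SDd
- power from the two-sided paired t test at 0.05

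| Assumed r | SDd (mm) | Limits (mm) | CI of mean (mm) | CI of each limit (mm) | Power, 0.11 mm | Power, 0.04 mm |
|---|---|---|---|---|---|---|
| 0.5 | 0.360 | ±0.71 | ±0.050 | ±0.085 | 0.99 | 0.35 |
| 0.7 | 0.279 | ±0.55 | ±0.039 | ±0.066 | >0.99 | 0.52 |
| 0.8 | 0.228 | ±0.45 | ±0.032 | ±0.054 | >0.99 | 0.70 |
| 0.9 | 0.161 | ±0.32 | ±0.022 | ±0.038 | >0.99 | 0.94 |

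For 0.04 mm, power is 0.81 at r = 0.85, so 80% is reached only at about that correlation or higher.

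**5. Number of comparisons.** From the Visit Schedule, the comparisons with the Orbscan II are WTW 8, ACD 5 and CT 6, or 19 in all before any added devices. With Bonferroni over 19 (normal approximation), power for 0.11 mm is still 0.91 at r = 0.5 and 0.99 at r = 0.7.

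**6. Two eyes.** If 400 eyes are treated as independent, the standard error is understated by √(1 + k), where k is the inter-eye correlation of the differences (assumed). At k = 0.5 the factor is 1.22 and the effective n is 400/1.5 = 267. At k = 0.8 it is 1.34 and 400/1.8 = 222.

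**The case against.** The strongest reply is that correlation is a declared aim, not a slip. The Scientific Rationale and Study Objectives both state it, so the endpoint follows one of two aims that the document holds at once. This is correct as description, and it means the Rationale must be aligned too. It does not rescue the endpoint: the Evaluation Criteria make the difference the main objective, and the hypothesis and sample size follow that aim.

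A second reply is that *correlation* is loose wording for agreement and that differences are plainly intended, since the study is called comparative. That may be so, but nothing in the text puts the intention into practice. No analysis of any kind is specified, for correlation or for differences.

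A third is that this is a one-visit observational study whose paired data will exist anyway, so no information is lost. That stands, and it is why the remedy is cheap. The remaining risk is an uninformative or selectively chosen primary result.

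Three further limits are fair. The size estimates cover WTW only, because the plan gives no SD for ACD or CT. They also depend on assumed correlations and equal SDs. Finally, the Orbscan II mean is cited to a different source from the other two means, so 0.11 and 0.04 mm may not be true paired offsets.

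**Conclusion.** The concern holds. Reported exactly as written, the sole primary endpoint would leave the hypothesis and main objective unanswered, because an ordinary correlation is the same with or without the 0.11 mm difference that sized the study. This conclusion needs no assumed figure. It follows from the wording and from the arithmetic behind the 168 eyes.

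The spread, precision and power figures do rest on assumption: SD 0.36 mm on both devices, a between-device correlation of 0.5 to 0.9, and one data point per patient. On that basis 200 patients are ample for a paired 0.11 mm WTW difference. They are adequate for 0.04 mm only if the devices are highly correlated. The fault lies in the endpoint and the missing analysis; the design can answer the question.

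**What to change.** 1. Make the primary endpoint the within-eye difference, device minus Orbscan II, for each measure and device. Report the mean difference with 95% CI, Bland-Altman 95% limits of agreement with CIs, and a check for proportional bias.
2. Fix the handling of two eyes in advance. One option is one eye per patient by a pre-stated rule for the primary analysis, which fits the count of 200 data points. Both eyes then go into a supporting mixed model with patient as random effect, or an analysis with patient-clustered errors. A clustered primary analysis of both eyes is also defensible; the choice must be written down.
3. Define *standard difference* as this quantity. Use the same wording, with the Orbscan II as reference, in the Scientific Rationale, Study Objectives, main objective and primary endpoint.
4. Keep correlation as secondary and name the coefficient.
5. Name WTW, the only measure sized, as the lead measure and report the rest as estimates with CIs; otherwise adjust for the 19 planned comparisons. Say how any added device will be treated.
6. Restate the sample size on a paired basis, giving the expected precision and the assumptions behind it. State that the 0.04 mm Pentacam difference is adequately powered only at high between-device correlation.

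The cost is a short analysis section, wording changes in four places, a rewritten sample-size paragraph and the reporting of 19 comparisons. No patients, visits or devices are added. It should be done before the analysis starts.
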